[[To test the efficacy of a group-based education and skill-building rehabilitation (ESBR) intervention in improving dementia caregiver and care recipient outcomes, our proposed trial will consist of 150 family caregivers coping with all-cause dementia. Fifty participants will be randomized to receive in-clinic ESBR (ESBR-i), 50 participants will be randomized to receive video telehealth ESBR (ESBR-v), and 50 participants will be randomized to receive usual care plus supplemental educational materials on dementia (UC).]]

The current proposed project will recruit family caregivers of Veterans with all-cause dementia to participate in a randomized, controlled trial of a group-based ESBR designed to enhance quality of life for caregivers of Veterans with all-cause dementia (Primary Aim 1), reduce caregiver depression (Secondary Aim 2), and **[[increase community tenure]]** and delay permanent long-term care placement and mortality of Veterans with all-cause dementia (Secondary Aim 3). Video telehealth technology (ESBR-v) or in-clinic contact (ESBR-i) will be used to deliver the caregiver intervention to family caregivers. ESBR groups will be compared to participants who receive usual care supplemented with educational materials on dementia (UC). Intervention effects will be examined longitudinally using mixed effects modeling and Cox proportional hazards models at six, 12, and 24 months post-intervention.

The results of this project will determine the efficacy of a low-cost, pragmatic intervention for caregivers of Veterans with all-cause dementia and will be used to build upon prior findings indicating the efficacy of resource-intensive methods to rehabilitate caregivers of Veterans with Alzheimer’s disease.

The table below presents a general outline of the activities planned during the award period to ensure timely completion of the research plan, publication/presentation of results, preparation of future studies aiming to enhance Veteran- and family-centered care (i.e., VA Merit Award), and development of a dissemination/implementation plan for a successful intervention.

CDA-2 TIMELINE										
	Year 1		Year 2		Year 3		Year 4		Year 5	
Project Component										
Study preparation	X									
Recruit/screen participants	X	X	X							
Data collection		X	X	X	X	X	X	X	X	
Data analysis			X	X	X	X	X	X	X	
Manuscript preparation				X	X	X	X	X	X	X
Presentation of findings				X	X	X	X	X	X	X
Merit award preparation							X	X	X	X

2.A.3.b. Participants

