Inclusion criteria -- Participants must:

- be adults (age ≥18)
- report distress associated with being the primary caregiver for a family member with all-cause dementia [23]
 - **[[reporting at least 2 of the following 6 items at baseline assessment: felt overwhelmed, felt like they often needed to cry, were angry or frustrated, felt they were cut off from family or friends, reported moderate to high levels of general stress, or felt their health had declined]]**
- **[[provide at least one hour of care (supervision or direct assistance) per week over the past 3 months (other sources of caregiving for the Veteran with dementia can also be utilized; e.g., respite, home health aide, other family members, etc.)]]**
- be proficient in spoken and written English
- be capable of providing informed consent

Exclusion criteria -- Potential participants will be screened and excluded for:

- current or lifetime history of any psychiatric disorder with psychotic features
- prominent suicidal or homicidal ideation
- having met DSM-IV criteria for drug or alcohol abuse or dependence (except nicotine) within the past six months
- presence of alcohol intoxication (by breathalyzer) or alcohol withdrawal (by exam) during study recruitment or participation
- diagnosis of probable or possible dementia
- a Telephone Cognitive Screen score of < 20
- participation in another caregiver intervention within the past year
- lack of regular access to a telephone
- illness that would prevent 24 months of study participation
- planned transfer of care receiver to another caregiver or nursing home within 12 months

2.A.3.c.1. Recruitment

We aim to recruit 150 participants who meet inclusion/exclusion criteria for the proposed project (ESBR-i: n = 50; ESBR-v: n = 50; UC: n = 50). Participants will be recruited primarily from the VA Palo Alto Health Care System (VAPAHCS), including major divisions (i.e., Palo Alto, Menlo Park, and Livermore) and community-based outpatient clinics (CBOCs) in the surrounding area (i.e., Capitola, Fremont, Modesto, Monterey, San Jose, Sonoma, and Stockton). We anticipate primary referral sources to include: Sierra-Pacific Mental Illness Research Education and Clinical Center (directed by [name]); VAPAHCS Dementia Committee (chaired by [name], consultant); VA Memory Clinic (directed by [name]); Geriatric Research, Education, and Clinical Center ([name], consultant, serves as Clinical Nurse Specialist at this Center); Stanford/VA Aging

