Telephone Cognitive Screen (T-CogS)T. The T-CogS was originally referred to as the Telephone Mini-Mental State Examination (TMMSE) [42]. The T-CogS is a 26-item, brief mental status examination that was designed to be administered over the telephone, based on the Mini-Mental Status Examination (MMSE) [43]. Scores range from 0-26. Scores on the T-CogS are strongly correlated with MMSE scores ($r = 0.88$, $p < 0.001$) [44]. An exclusion cutoff score of < 20 on the T-CogS was chosen to match a MMSE cutoff of < 23 . A telephone cognitive screen was specifically chosen to reduce travel burden for caregivers. **[[Caregivers with a T-CogS score < 20 during screening, or any point during the study, will be offered referrals to the Stanford/VA Alzheimer's Research Center, with full support from Drs. [name] (Director) and [name] (Co-Director and CDA-2 Primary Mentor). The Center provides a comprehensive diagnostic evaluation, including cognitive assessment, by a multidisciplinary clinical research team at no cost to the patient.]]**

The results of all screening assessments will be review with Drs. [name] and [name] in consultation with Drs. [name] and [name]. After consensus determination of study eligibility, the Study Coordinator will contact the participant to schedule a Baseline assessment (if eligible), or provide appropriate referral (e.g., VA Caregiver Support Program) and explanation (if not deemed eligible). Both “screen failures” and eligible participants who drop out prior to receiving any intervention will be replaced.

2.A.3.e. Procedures Involving Eligible Participants

2.A.3.e.1. Enrollment, Randomization, and Baseline Measures

Enrollment and Randomization

Once participants pass screening, they will be invited by the Study Coordinator to participate in the study, if willing and able to provide informed consent *F*. At this point, the Data Manager will **[[randomize the participant to one of the three arms: ESBR-i, ESBR-v, or UC.]]** For randomization, a modification of the Efron procedure [45] developed by [name] [46] will be implemented to assure the three groups are comparable at baseline in terms of dementia subtype. Participants who drop out after receiving any intervention will not be replaced, but their data will be used in mixed-effects analyses (as described in Section 2.A.3.e.8a.).

Baseline Assessment

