Trained study staff, blind to the participants’ ESBR/UC assignment, will administer a baseline assessment including clinicodemographic updates and measures of caregiver burden, depression, self-efficacy, and health-related quality of life, in addition to care recipient functional status (see section 2.A.3.e.6. for a detailed description of these measures). These assessments will mainly occur over the telephone. Our motivation for telephone assessment is to reduce study participation burden for the participants. Packets with assessment aids will be sent to the caregiver in the mail prior to each assessment. **[[Should caregivers prefer, in-person assessments will also be offered.**

Mental Health referrals to Stanford Outpatient Psychiatry Clinics will be offered to all participants who score 16+ on the CES-D at any assessment (see Section 2.A.3.e.6), in addition to participants who endorse symptoms of significant clinical concern, as determined by study staff. All participants are also provided information on accessing the VA Caregiver Support Program and the Veterans Crisis Line.]]

2.A.3.e.2. Education and Skill-Building Rehabilitation Intervention (ESBR)

Our ESBR intervention consists of four, 90-minute sessions over a 4-6 week period. **[[These four sessions are supplemented with booster sessions at 3 and 9 months post-intervention.]]** Each group session (\leq 10 participants) is attended either in-clinic or via video telehealth technology within the VAPAHCS.

As presented in the Summary of Section 2.A.1.D., the two modifiable risk factors for dementia care recipient placement in LTC are caregiver burden and depression.

Caregiver Burden

Our ESBR intervention consists of four, 90-minute sessions **[[plus booster sessions at 3 and 9 months post-intervention]]**. Each group (\leq 10 participants) session is attended either in-clinic or via video telehealth technology in place at community-based outpatient clinics, or other VA facilities, throughout VAPAHCS. ESBR is designed to decrease caregiver burden by altering caregiver perceptions of burden through education on dementia from several perspectives including: 1) simplified science that non-professionals care relate to and process; 2) reframing of cognitive, behavioral, and psychiatric symptoms of dementia as manifestations of damage to the brain of their loved one; and 3) understanding access to and being connected with VA, community, and national resources that can assist with reducing burden.

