
- review dementia and dementia resources (~20 minutes)
- polish caregiving skills (tailored to the needs of each small group) (~35 minutes)
- re-emphasize the importance of self-care (~15 minutes)
- highlight learned relaxation techniques (~20 minutes)

The booster sessions are designed to briefly review dementia knowledge and resources available to dementia patients and their caregivers (i.e., within VA, the local community, and the nation). Caregiving skills, as they pertain to current stressors, are honed in a manner that is tailored to the small group's needs. The importance of continued self-care (specifically stress awareness, sleep hygiene, and planned pleasant activities) is accentuated. Intervention relaxation techniques (i.e., guided imagery, deep breathing, and progressive muscle relaxation) are revisited and continued use is fostered.]]

2.A.3.e.3. Method of Delivering ESBR as In-clinic or Video Telehealth

For the participants randomized to our ESBR intervention (n=50 in-clinic, ESBR-i; n=50 via video telehealth, ESBR-v), all ESBR sessions will be led by [name] in groups of ≤ 10 participants. Dates and times of the group intervention will be arranged to fit participant schedules. In general, Sessions 1-4 (described above) will

be completed within 4-6 weeks. Materials (e.g., print items, audio) for each session will be provided for each participant in each intervention arm.

In-clinic ESBR Delivery: Participants in the ESBR-i (in-clinic) group will meet in person with [name] to receive the ESBR intervention. They will come to the VAPAHCS medical center division (i.e., Palo Alto, Menlo Park or Livermore) or VAPAHCS community-based outpatient clinic (CBOC) in the proximal community (e.g., San Jose, Fremont) most convenient to them.

Video Telehealth ESBR Delivery: Participants in the ESBR-v (video telehealth) group will receive [name] ESBR intervention via video telehealth technology (i.e., two-way audio and video). Clinics throughout the VAPAHCS are equipped with private rooms containing with audio/visual equipment (video camera, microphone, and display monitor) that will be used to deliver the ESBR intervention with the assistance of the local telehealth coordinator. Participants will attend the ESBR sessions at the medical center division or CBOC most convenient to them.

2.A.3.e.4. Usual Care (plus supplemental educational materials)

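### Replacement and data use turn on receiving intervention, not on randomization, so as worded randomized caregivers who leave before session 1 are replaced and not promised analysis

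*Combined protocol and SAP*

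**What the plan says.** Two sentences govern early dropout, and both draw the line at the same event.

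- The end of Section 2.A.3.d (Screening Procedures) says, alongside screen failures, that "eligible participants who drop out prior to receiving any intervention will be replaced".
- Section 2.A.3.e.1 (Enrollment and Randomization) says: "Participants who drop out after receiving any intervention will not be replaced, but their data will be used in mixed-effects analyses".

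Between them, Section 2.A.3.e.1 has the Data Manager "randomize the participant to one of the three arms: ESBR-i, ESBR-v, or UC" once screening is passed and consent given. The ESBR sessions come later, in groups of at most 10. Section 2.A.3.e.3 says of them: "Dates and times of the group intervention will be arranged to fit participant schedules".

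Section 2.A.3.e.8a cites intention to treat as a reason for the mixed model. Hypotheses 3b and 3c time long-term care placement and death from randomization. No section defines an analysis set, and none says what becomes of a randomized caregiver who never attends a session.

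**The concern.** A trial may replace people freely until they are randomized. After that, replacing and dropping them makes membership of the comparison depend on something that happened after assignment. Here that event is unlikely to be equally common in the arms. ESBR caregivers wait for a group and then attend a VA site, in the video arm as well as the in-clinic arm. Usual-care caregivers receive printed materials. Caregivers who leave during the wait may also differ from the rest in burden, which is the primary outcome.

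A likelihood analysis under missing at random does not repair this, because it covers only people who are in the data set. The primary ZBI comparison, the CES-D comparison and the time-to-event comparisons would all be affected.

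**Working it through.** **1. Who falls under which rule.** The order in the text is screening, consent, randomization, then sessions.

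| Caregiver leaves | Replaced? | Data used? |
|---|---|---|
| As a screen failure | Yes | Not applicable |
| Eligible, before randomization | Yes | No assigned arm, so no intention-to-treat issue |
| Randomized, before session 1 | Yes, as worded | Not stated |
| After some intervention | No | Yes |

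The third row is the defect. Nothing confines replacement to the second row, and the promise of analysis reaches only the fourth.

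**2. Is the third row populated equally by arm?** For ESBR, the wait between randomization and session 1 has no stated length. For usual care, Section 2.A.3.e.5 dates follow-up from assignment, which suggests little or no period before intervention. The row is therefore likely to hold mainly ESBR caregivers.

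**3. Consistency with the rest of the plan.** Section 2.A.3.a describes 50 per arm as the number randomized. If randomized leavers are replaced, the number randomized is 150 plus the number replaced, with no stated limit.

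**4. Order of baseline and randomization.** The sections point different ways.
- Section 2.A.3.b defines the distress criterion as "reporting at least 2 of the following 6 items at baseline assessment", which suggests that baseline precedes the eligibility decision.
- Section 2.A.3.d has all inclusion criteria checked in the screening interview, and the Assessment Timeline marks inclusion and exclusion only under screening.
- Section 2.A.3.d then only schedules baseline for those found eligible.
- Section 2.A.3.e.1 describes baseline after randomization, by staff blind to the participants' "ESBR/UC assignment, will administer a baseline assessment".

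If randomization comes first, an early leaver may have no baseline ZBI.

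**5. Size of the bias.** Let p be the proportion of an arm left out before session 1, and δ the mean outcome of starters minus that of non-starters, in SD. The as-randomized mean is (1 − p) × starters + p × non-starters, so leaving non-starters out shifts the arm mean by p × δ. The bias in the ESBR minus UC difference is p(ESBR) × δ(ESBR) − p(UC) × δ(UC). The documents give none of these four values.

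As an illustration only, assume p(UC) = 0, p(ESBR) from 5% to 20%, and δ from 0.2 to 0.5 SD in absolute value:
- Low end: 0.05 × 0.2 = 0.01 SD, and 0.01 / 0.3 = 3% of the planned effect of d = 0.3.
- High end: 0.20 × 0.5 = 0.10 SD, and 0.10 / 0.3 = 33% of it.

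The sign follows the sign of δ, which is unknown. The plan's attrition allowance (10%, 15% and 20% at 6, 12 and 24 months) does not measure this. It is general loss to follow-up, and Section 2.A.3.e.8b does not say whether pre-session leavers count in it.

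**6. Power if never-starters are kept.** The stated power of 0.83 (d = 0.3, 100 against 50, two-sided 0.05) can be reproduced as 0.823. This uses a piecewise growth model with the stated attrition and three assumptions of mine: a knot at 6 months, equal baseline means, and a constant correlation of 0.7 taken from the stated reliability. The standard error at 12 months is then 0.104 SD. If a proportion p of ESBR is followed but gains nothing, the effect is 0.3 × (1 − p) and power is Φ(0.3 × (1 − p) / 0.104 − 1.96):

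| Assumed p | Effect d | Power |
|---|---|---|
| 5% | 0.285 | 0.78 |
| 10% | 0.270 | 0.74 |
| 15% | 0.255 | 0.69 |
| 20% | 0.240 | 0.64 |

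These figures rest on assumed p and on my reconstruction of the plan's model.

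**The case against.** The best defence is where the rule stands. It closes the screening section, next to screen failures and before randomization is mentioned, so it may have been meant only for people not yet randomized. Replacing someone is also not the same as excluding their data. The intention-to-treat statement, the outcomes timed from randomization and the target of 50 randomized per arm all fit an analysis of everyone randomized. This stands as a plausible account of intent. It does not settle the text, because the companion sentence sits in the randomization section and uses the same boundary of having received intervention.

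A reader might infer three stronger things that the documents do not support.

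- That the plan excludes randomized non-starters. No section says their data are removed; exclusion is implied only by reading the two sentences together.
- That the plan places baseline before randomization. One phrase in the inclusion criteria points that way, but the screening interview, the Assessment Timeline and the blinding statement do not.
- That never-starters have no follow-up dates and that usual care has no defined start. The end of an assigned group can serve as the end of intervention, and follow-up in usual care runs from assignment. Only an ESBR caregiver never placed in a group clearly lacks a date.

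Keeping these caregivers in the analysis is also no complete cure. Someone who leaves entirely will probably lack later ZBI and CES-D scores under either rule. Community tenure can also draw on available medical records, but placement and death are described as learned from the caregiver.

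**Conclusion.** The point holds as a defect of wording that touches the primary comparison. Followed literally, the plan replaces randomized caregivers who leave before session 1 and promises analysis only for those who leave later. Whether it would be applied that way, and whether the replaced caregivers would then be omitted, is left open. Any harm depends on both.

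The size and direction of the bias cannot be determined from the documents. Under the assumed ranges above it runs from negligible to about a third of the planned effect. Unequal exposure by arm is an inference from how ESBR and usual care are delivered, not a reported rate. It should be fixed because the change is small and removes the ambiguity; confidence is medium because the intended meaning may already be the right one.

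**What to change.** 1. Limit replacement to people who leave before randomization.
2. State that every randomized caregiver is analysed in the assigned arm with all available data. Keep offering the existing 6-, 12- and 24-month telephone assessments to those who never start but have not withdrawn consent. Date these, for example, from the end of the assigned group, or from randomization if no group was assigned.
3. Report pre-session dropouts by arm.
4. Reconcile Sections 2.A.3.b, 2.A.3.d and 2.A.3.e.1 and the Assessment Timeline on the order of screening, baseline and randomization. Preferably complete baseline before randomization, so that early leavers have a baseline ZBI.

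The cost is a few sentences of text and a few more telephone calls. If baseline moves first, some of those calls will go to people who are then not randomized. Following never-starters who receive no ESBR dilutes the effect and costs some power, by an amount the documents do not allow to be calculated. If enrolment is already complete, items 2 (the analysis set) and 3 can still be adopted.

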Participants randomized to the Usual Care (UC) group will receive supplemental educational materials (e.g., VA Caregiver Support Program, Veterans Crisis Line, National Institute on Aging publications "Caring for a Person with Alzheimer's Disease: Your Easy-to-Use Guide" and "Understanding Memory Loss").

2.A.3.e.5. Follow-up (at 6, 12, and 24 months post-intervention)

Trained study staff, blind to the participants' ESBR/UC assignment, will administer follow-up assessments at 6, 12, and 24 months after the conclusion of the intervention or assignment to usual care. These assessments will mainly occur over the telephone. Our motivation for telephone assessment is to reduce study participation burden for the participants. Packets with assessment aids will be sent to the caregiver in the mail prior to each assessment. **[[Should caregivers prefer, in-person assessments will also be offered.]]** The follow-up assessments include clinicodemographic updates and measures of caregiver cognitive status, burden, depression, self-efficacy, and health-related quality of life, in addition to care recipient functional, placement, and mortality status. (See section 2.A.3.e.6. for a detailed description of these measures).

[[2.A.3.e.6. Study Conclusion

At the conclusion of the study, all participants will be thanked for their participation. Similar to referral procedures implemented throughout the study, at the conclusion of the study all participants will be provided with referrals for services for significant stress, mental health challenges, or cognitive concerns. Mental Health referrals to Stanford Outpatient Psychiatry Clinics will be offered to all participants. Participants with cognitive concerns will be offered referrals to the Stanford/VA Alzheimer's Research Center. The Center provides a comprehensive diagnostic evaluation, including cognitive assessment, by a multidisciplinary clinical research team at no cost.]]

2.A.3.e.6. Study Measures

Study assessments will mainly occur over the telephone τ , conducted by the Study Coordinator. Our motivation for telephone assessment is to reduce study participation burden for the participants. Packets with assessment aids will be sent to the caregiver in the mail prior to each assessment. **[[Should caregivers prefer, face-to-face (in-person) τ assessments will also be offered.]]**

Primary Outcome: Caregiver Burden

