Zarit Burden Interview (ZBI) [58] τ . The ZBI is a 22-item self-report measure of caregiver burden. Several version of the ZBI have been used successfully as outcome measures in interventions for dementia caregivers [22, 23, 40]. Reliability of the ZBI ranges based on time intervals between tests, but can be assumed to have moderate reliability [59-61]. The ZBI contains questions related to emotional, physical, and social strains that result from caregiving. Scores for each item range from 0 (never) to 4 (nearly always) on questions such as "Do you feel embarrassed by your relative's behavior?" Total scores are calculated by summing all responses and range from 0-88.

Secondary Outcome: Caregiver Depression

Center for Epidemiological Studies-Depression (CES-D) [62] τ . The CES-D is a 20-item, self-report measure of frequency of depressive symptoms over a one week period. The CES-D is frequently used to assess depression in dementia caregivers and has been shown to be sensitive to changes in caregiver depression post intervention [37]. It has been demonstrated to show sufficient psychometric properties [62]. Scores for each item range from 0 (rarely or none of the time) to 3 (most or all of the time), with some items reverse coded. Total scores are calculated by summing all responses and range from 0-60. A cutoff score of $>$ or $=$ 16 is used to indicate depressive symptoms considered to be comparable to prevalent depression.

[[Secondary Outcome: Community tenure τ

Based on caregiver interview and available medical records, community tenure (i.e., amount of time spent living in the community and not hospitalized or placed in a facility) and number of incidents leading to non-community status will be ascertained.]]

Secondary Outcome: Long-term Care Placement τ

Based on caregiver interview, permanent placement of the care recipient in LTC will be ascertained at all follow-up time-points. Date and level of placement will be ascertained.

Secondary Outcome: Mortality τ

Based on caregiver interview, care recipient mortality status will be ascertained at all follow-up time-points. Date and cause of death will be ascertained.

Supplementary Outcomes

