Hypothesis 3a. Mixed effects modeling will be used to test the hypothesis that participants randomized to the intervention groups (ESBR-i and ESBR-v) will show longer community tenure compared to UC over time. In mixed effects analyses, days of community tenure will be modeled as the key dependent variable predicted by the group membership (ESBR-i and ESBR-v vs. UC). The model will be adjusted for effects of care recipient gender, income, and disease stage (Global Deterioration Scale score). The effects of other potential covariates including caregiver and patient age, caregiver gender, dementia subtype, and caregiver burden and depression will also be explored.

Hypothesis 3b. Cox proportional hazards regression modelling [70] will be used to test the hypothesis that Veterans with family caregivers randomized to the intervention groups (ESBR-i and ESBR-v) will transition to LTC at a slower rate compared to UC. In proportional hazards regression analyses, time to permanent LTC placement (total time from caregiver randomization to permanent LTC placement of the care receiver) will be modelled as the key dependent variable predicted by the group membership (ESBR-i and ESBR-v vs. UC). The model will be adjusted for effects of care recipient gender, income, and disease stage (Global Deterioration Scale score). The effects of other potential covariates including caregiver and patient age, caregiver gender, dementia subtype, and caregiver burden and depression will also be explored.

Hypothesis 3c. Cox proportional hazards regression modelling [70] will be used to test the hypothesis that Veterans with family caregivers randomized to the intervention groups (ESBR-i and ESBR-v) will survive longer compared to UC. In proportional hazards regression analyses, time to death (total time from caregiver randomization to death of the care receiver) will be modelled as the key dependent variable predicted by the group membership (ESBR-i and ESBR-v vs. UC). The model will be adjusted for effects of care recipient gender, income, and disease stage (Global Deterioration Scale score). The effects of other potential covariates including caregiver and patient age, caregiver gender, dementia subtype, and caregiver burden and depression will also be explored.

Exploratory Aims:

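### Follow-up starts at different points in ESBR and UC, and Hypothesis 3a counts raw days of community tenure with no start date or common window, so tenure can differ between arms with no treatment effect

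*Combined protocol and SAP*

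**What the plan says.** - **Visit timing.** Section 2.A.3.e.5 states that blinded staff "will administer follow-up assessments at 6, 12, and 24 months after the conclusion of the intervention or assignment to usual care". UC receives printed materials only (2.A.3.e.4), so its clock starts at assignment. The ESBR clock starts after the last of the four sessions.
- **Length of the sessions.** Section 2.A.3.e.2: "Our ESBR intervention consists of four, 90-minute sessions over a 4-6 week period". Section 2.A.3.e.3 says that the sessions will in general "be completed within 4-6 weeks", and adds: "Dates and times of the group intervention will be arranged to fit participant schedules". No limit is set on the wait between randomization and the first session. All three arms are randomized at the same earlier step (2.A.3.e.1).
- **Community tenure.** Section 2.A.3.e.6, Study Measures, defines it as the "amount of time spent living in the community and not hospitalized or placed in a facility". The assessment timeline lists it at baseline and at 6, 12 and 24 months, with no look-back period.
- **Analysis.** Under Hypothesis 3a in 2.A.3.e.8a, "days of community tenure will be modeled as the key dependent variable predicted by the group membership", adjusted for care recipient gender, income and disease stage. Days observed do not enter. Hypothesis 3b, by contrast, uses the "total time from caregiver randomization to permanent LTC placement of the care receiver", and 3c likewise starts at randomization.

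**The concern.** Tenure is an amount of time, so its value depends on when counting starts and stops. With visits dated from different events in the two conditions, visits with the same label sit at different distances from randomization. The plan does not say whether tenure accumulates from randomization, from each arm's own follow-up origin, since the previous visit, or over a fixed look-back. These rules give null differences of different size and sign.

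Longer community tenure is part of Secondary Aim 3. The power section (2.A.3.e.8b) says that secondary results will be judged more on effect size than on p-values and will guide later trials. A difference of some weeks produced by the clocks alone could be carried forward as a benefit of ESBR.

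**Working it through.** The plan gives no figure for tenure to reproduce. Its one power figure (0.83) concerns ZBI and plays no part here.

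**Inputs**
- Offset d = 28 to 42 days, from the 4-6 weeks in 2.A.3.e.2 and 2.A.3.e.3. Any wait for a group would be added; it is unknown and set to 0.
- Visit times T = 182.6, 365.25 and 730.5 days (6, 12 and 24 months).
- Permanent exit from the community at p = 10% to 40% a year, constant and equal in all arms. This is an assumption; the documents give no rate.

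**Offset as a share of follow-up**
- 6 months: 28/182.6 = 15.3% to 42/182.6 = 23.0%
- 12 months: 28/365.25 = 7.7% to 42/365.25 = 11.5%
- 24 months: 28/730.5 = 3.8% to 42/730.5 = 5.7%

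**Expected tenure with no treatment effect**

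Daily hazard L = -ln(1-p)/365.25, which is 0.000288 at 10% and 0.001399 at 40%. Expected community days between day a and day b are I(a,b) = [exp(-La) - exp(-Lb)]/L. The null difference, ESBR minus UC, is:
- randomization to each visit: I(0,T+d) - I(0,T)
- each arm's own origin: I(d,T+d) - I(0,T)
- since the previous visit: the first interval as in the first rule, then I(Tprev+d,T+d) - I(Tprev,T)
- fixed look-back, 182 days as an example: I(T+d-182,T+d) - I(T-182,T)

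Examples:
- First rule, 6 months, p = 10%, d = 42: 217.50 - 177.90 = +39.6 days.
- First rule, 6 months, p = 40%, d = 28: 182.44 - 161.17 = +21.3 days.
- Second rule, 24 months, p = 40%, d = 42: 431.51 - 457.61 = -26.1 days.

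| Counting rule | 6 months | 12 months | 24 months |
|---|---|---|---|
| Randomization to each visit | +21.3 to +39.6 | +16.5 to +37.6 | +9.9 to +33.8 |
| Each arm's own origin | -1.4 to -9.2 | -2.8 to -16.3 | -5.3 to -26.1 |
| Since previous visit | +21.3 to +39.6 | -1.4 to -7.1 | -2.5 to -9.8 |
| 182-day look-back | -1.4 to -9.2 | -1.4 to -7.1 | -1.2 to -4.3 |
| Same fixed windows from randomization | 0 | 0 | 0 |

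**Other cases**
- With no exits at all, the first rule gives +28 to +42 days at every visit. The since-previous-visit rule gives this at month 6 only, then 0. The other two rules give 0.
- If care recipients spend a constant share q of the time in temporary stays, expected tenure over a window of length W is (1-q)W. Equal windows then differ by 0, whenever they start. Only a longer window gives a gap, of (1-q)d.

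**What a test would do under the first rule**

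With 100 ESBR and 50 UC, 20% or 30% annual permanent exit and no attrition, a simulated two-sided 5% t-test of visit means rejected in 81-100% of null trials at 6 months, 16-48% at 12 and 6-10% at 24. With fixed common windows it rejected in 4.5-5.3%.

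**Primary outcome**

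If ZBI drifts by 0.1 to 0.3 SD a year in either direction (assumed), the offset moves the 12-month contrast by 0.1 x 28/365.25 = 0.0077 to 0.3 x 42/365.25 = 0.0345 SD, against a planned effect of 0.3.

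**The case against.** The best reply is that the largest figures belong to a rule the plan may not intend. The assessment timeline lists tenure at baseline. A count starting at randomization is zero there by definition, so a baseline value suggests a look-back, and a fixed look-back gives equal windows. This stands as evidence about intent, but no look-back length is written anywhere, so the rule remains open.

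Second, the negative figures come from permanent exits. Tenure also covers hospital stays, which are usually temporary, and equal windows are unbiased for these at a constant rate. Planned nursing-home transfer within 12 months is an exclusion (2.A.3.b), which makes high early exit rates less likely. A reader might infer that every counting rule carries the offset; for this reason that inference is too strong.

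Third, the analysis is a growth model, not a comparison of raw means. That is fair, but 2.A.3.e.8a does not say how time is coded, and it intends to convert the model to a group effect at each assessment. If time is coded by visit label, those effects inherit the gap. With no exits the first rule adds a constant after month 6, so slopes from 6 to 24 months would agree, while the change from baseline to month 6 would not.

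A reader might also infer that the primary analysis is compromised. It is not: a ZBI score does not accumulate with time, and timing it from the end of the intervention is a legitimate choice.

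**Conclusion.** The point holds for Hypothesis 3a, in the comparison of pooled ESBR with UC. The two clocks are stated in the plan and the outcome is raw days, so this is more than an unwritten definition. It remains a cheap improvement to a secondary outcome.

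The documents do not support saying that 3a is bound to favour ESBR. The gap of three to nearly six weeks at 6 months arises if the first count runs from randomization or baseline to the visit. With equal windows the gap goes against ESBR and is smaller at 6 and 12 months. At 24 months the own-origin count can reach -26.1 days, but only at 40% annual permanent exit and a 42-day offset. It is near 0 when absences are temporary and constant in rate.

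All sizes are differences in raw visit means. They rest on the assumed exit rates and on no wait for a group; a wait would widen the offset. Hypotheses 3b and 3c are unaffected, and ESBR-i and ESBR-v share one follow-up origin.

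**What to change.** In the tenure definition (2.A.3.e.6, Study Measures) and in Hypothesis 3a:

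- Count tenure from randomization in every arm over the same fixed windows, for example days 0-182, 0-365 and 0-730, including the session period.
- Record the start and end date of each hospital or facility stay so that the windows can be built. For permanent placement the plan already says "Date and level of placement will be ascertained", and date of death is also planned.
- State that the tenure estimand then runs from randomization, as in 3b and 3c, and not from the end of the intervention.
- Where a window is incomplete, analyse the share of observed days spent in the community, or use an observed-days offset.
- State how time is coded in the 3a model, and what the baseline tenure entry measures.

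Leave visit timing and the ZBI analysis as planned. No visit has to move: ESBR visits fall at about days 211-225, 393-407 and 759-773, and UC visits at about days 183, 365 and 730. The first two windows can be completed from dates collected at a later visit.

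The cost is stay dates on the tenure form and a little more analysis work. The weak spot is the final UC visit, which has almost no margin over day 730. An early visit leaves that window short, which is why the observed-days rule is needed.
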